7.4. Resource Use

(i) Resources associated with administration of treatment in both arms (including materials used and time and grade of staff involved in fitting/removing the plaster/boot and providing the necessary instruction to patients) will be captured by the research team in the CRF at the 2 week post-surgery (baseline) and 6-week post-surgery (4 week post-randomisation) appointment in clinic.

(ii) Resources delivered by the treating hospital¹ at 10 weeks from randomisation will be collected from a review of patients' hospital notes at the end of the patient's participation. Data on inpatient admissions, outpatient appointments and outpatient therapies provided, as well as diagnostic tests performed will be collected onto CRF's by the research team from randomisation (2-week post-surgery) until last follow-up (12 weeks post-surgery). Date of event will be collected, to allow for costing the two different periods of resource use, in the two economic analyses.

¹ In this context, 'treating hospital' refers to the hospital in which the ankle fracture surgery is performed.

(iii) Participants' use of other health and social care resources, as well as informal care and loss of productivity, will be captured at the 4-week and 10-week time points via patient-completed questionnaires. Patient reported data will be collected from randomisation on:

- (a) Community-based health care services used. This will include contacts with GP doctor and nurses at the GP practice, at home or by telephone, and other health services required such as community physiotherapist and occupational therapist visits. Use of concomitant medications will also be patient reported.
- (b) Secondary care visits to hospitals
- (c) Use of social services, such as home help, food at home services and contacts with social worker.
- (d) Productivity losses, including a measurement of absenteeism and presenteeism, by adapting a few questions from the Work Productivity and Activity Impairment Questionnaire (WPAI): General Health Version 2.0¹⁶, a licence-free, well-known and validated questionnaire commonly used to measure productivity losses when patients take time-off work or are unproductive at work¹⁷⁻¹⁸. We will also collect losses in leisure time and informal care from friends and relatives.
- (e) Private expenses, such as travel, privately paid therapies or lost income.

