9.3.2. Baseline questionnaire completion

After eligibility has been confirmed and written consent obtained, and prior to randomisation, patients will be provided with a questionnaire booklet to be completed during the visit. The baseline questionnaire booklet will comprise the following questions;

- Demographic and socio-economic questions
- Pre-injury Olerud and Molander (1984) ankle score (see section 7.1)
- EQ-5D-5L (see section 7.2)

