9.3.4. Randomisation

Following completion of baseline information collection, a member of the research team will randomise the participant to one of the two treatment groups; Removable support boot, or plaster.

Patients will be randomised in order to minimise systematic bias, using a secure web-based system designed and maintained by the Peninsula Clinical Trials Unit

(PenCTU) according to the Unit's standard operating procedures. Computer generated randomisation codes prepared by the PenCTU will be kept secure, with access restricted to the data management team at the PenCTU. Participants will be allocated to the support boot group (intervention) or to the plaster group (control) in a 1:1 ratio, using random, even, block sizes between 2 and 8 to generate the allocation sequence and achieve balance in the numbers of participants allocated to each group. Randomisation will be stratified by site. The web-based randomisation system will be accessed securely via unique log-in details provided to each local team member by the CTU. The system ensures that allocation is appropriately concealed until the point of randomisation.

Upon randomisation, each participant will be assigned a unique Trial Number which will be used as the principal identifier on trial data collection forms and questionnaires. The research team member will disclose the allocation to the participant and will ensure the allocation is followed as described below.

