The profiles from the patients’ answers to the EQ-5D-5L will be weighted using the EuroQol’s published United Kingdom societal utility tariffs to produce a composite, utility based quality of life score and EuroQol has piloted the 5L valuation scores²⁵. If final scores are not available by the end of the trial, the crosswalk developed by EuroQol from the three level scores will be used. Quality Adjusted Life Years will then be created from the four time point utility scores assuming a linear change between the time points and using the area under the curve approach. Incremental QALY gains between arms will then be estimated using regression analysis adjusted for baseline utility and site, age and fracture complexity variables.

Multiple regression will be used to investigate differences between the two groups in the other continuous outcomes measured at four weeks post-baseline (e.g. degrees of range of movement (dorsiflexion, plantarflexion, inversion, eversion), circumferential swelling and 10 weeks (e.g. return to daily activities on 0-10 scale). Complications in the two groups (presence and severity), healing status (displaced / undisplaced and evidence of post-operative fracture healing (yes/no)), employment status at 10 weeks, driving status and weight bearing status will be investigated using logistic regression (binomial or multinomial depending on the number of categories), again taking study site, age and fracture complexity into account. Survival analysis will be used to investigate the time from randomisation to starting to drive again. Supplementary analysis (b) to (e) as described for the primary outcome will also be conducted for secondary outcomes.)

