12.4. Economic Evaluation

The primary economic evaluation will compare the costs and health benefits of the support boot compared to plaster in short-term ankle fracture management from an NHS and Personal Social Services perspective. In sensitivity analysis, an economic evaluation from a societal perspective on costs will be performed.

The evaluation will be:

1. A cost-utility analysis at ten weeks post-randomisation; Quality Adjusted Life Years (QALYs) between arms will be compared to identify whether any treatment arm is dominant (i.e. less costly and more effective). If no arm is dominant, results will be presented as a bootstrapped incremental cost-effectiveness ratio (ICERs) with respect to QALYs gained. Bootstrapped estimates of costs and effects will be plotted in the cost-effectiveness plane. Incremental net monetary benefit statistics (INMB) will be derived using the £20,000 and £30,000 societal willingness to pay thresholds for a QALY. Cost-Effectiveness Acceptability Curves (CEACs) will be plotted to show the probability of the intervention being cost-effective at a range of societal willingness to pay thresholds, thus addressing uncertainty around the adoption decision. If one arm is dominant, ICERs are not meaningful and we will only report INMB statistics and plot the cost-effectiveness planes and CEAC.
2. A cost-effectiveness analysis at approximately 5 weeks post-baseline, coinciding with the collection of primary clinical outcome; Costs and Olerud and Molander scores between arms will be compared to identify whether any treatment arm is dominant. If no arm is dominant, results will be presented as a bootstrapped incremental cost-effectiveness ratio with respect to the Olerud and Molander¹⁴ scale. If the treatment arm is a dominant or dominated strategy, ICERs will be

negative and not meaningful. In that case, we will only report INMB statistics in relation to QALYs and will not proceed any further with the cost-effectiveness analysis with respect to the Olerud and Molander scale.

Collecting 5 week and 10 week resource use:

Resource use collection will take place as defined in above section “7.4 Resource Use” in this protocol.

At 10 weeks, resource use for the primary economic result will result from adding secondary care resource use collected from the review of 10 weeks of medical notes and the two resource use questionnaires at 4 weeks and 10 weeks.

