For the second economic result, the primary clinical outcome collected at approximately 5 weeks (4 weeks + 3-10 days) after randomisation will be compared with costs for the same period. We will identify the proportion of secondary care cost, collected from medical notes, taking place in the additional days post the 4 week clinic visit for the patient, and assume the patient would have an equal proportion of cost for the other cost categories, collected by questionnaire. This assumed incremental patient reported cost, will be added to the 4 week cost data collected from questionnaires and the corresponding period cost from medical notes, to compose a total patient cost from baseline to collection of primary clinical outcome data.

Valuing resources:

Resource use will be valued using unit costs for health and social care, department of health reference costs or other national routine sources²⁷⁻³⁰ whenever available. Trust finance departments will be contacted for procurement costs on the boot and plaster materials. Productivity losses will measure absenteeism and presenteeism and be valued using the human capital approach³¹⁻³² in the main analysis, and the friction costs approach in sensitivity analysis. Estimations will be adjusted for pre-randomisation work status and return to work.

Analysis of costs and outcomes:

Costs and QALYs (mean and confidence intervals) will be estimated using regression analysis, adjusting for site, age, and fracture complexity in addition to baseline utility for QALYs). We will ascertain whether the treatment arm would be dominant, i.e. less costly and more effective, or dominated, i.e. more costly and less effective, with respect to QALYs and the Olerud and Molander scale.

Missing data in the economic result:

Cost is cumulative and additive: missing data in one cost component at one follow-up time point means that the full cost per patient cannot be computed. A specific missing data strategy has been developed for the economic evaluation, in case of poor patient-completion of resource use questions.

Missing data will be imputed using multiple imputation methods, in a two-stage ordinary least squares model, adjusting for socio-demographic characteristics

collected at baseline. As the primary economic result are parameters (ICERs / NMB) relating Costs and QALYs, the imputation models will simultaneously include disaggregated cost categories and utilities.

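### Section 12.4 adjusts QALYs but not costs for baseline EQ-5D-5L utility; adjusting both would be a free, minor gain in precision for the cost difference and net monetary benefit

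*Protocol*

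**What the plan says.** Section 12.4, under the analysis of costs and outcomes, gives both regression models in one sentence: "adjusting for site, age, and fracture complexity in addition to baseline utility for QALYs". Costs are adjusted for three variables and QALYs for the same three plus baseline utility. Section 12.2.3 states the QALY model again, in agreement: "Incremental QALY gains between arms will then be estimated using regression analysis adjusted for baseline utility and site, age and fracture complexity variables".

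The same section builds the QALY as an area under the curve that includes the baseline score: "Quality Adjusted Life Years will then be created from the four time point utility scores assuming a linear change between the time points".

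The baseline EQ-5D-5L is part of a booklet given to patients, in the words of section 9.3.2, "After eligibility has been confirmed and written consent obtained, and prior to randomisation". Resource use is counted only from that point on; section 7.4 says of the questionnaire items, "Patient reported data will be collected from randomisation on". On allocation, section 9.3.4 says "Randomisation will be stratified by site".

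The two estimates are then combined. Section 12.4 says "Incremental net monetary benefit statistics (INMB) will be derived using the £20,000 and £30,000 societal willingness to pay thresholds for a QALY", and for uncertainty, "Bootstrapped estimates of costs and effects will be plotted in the cost-effectiveness plane".

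**The concern.** INMB is the threshold times the QALY difference, minus the cost difference. As written, its two parts come from models with different covariates. If the arms happen to differ in health at the baseline visit, the QALY part is corrected for that difference and the cost part is not.

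A patient's state two weeks after surgery plausibly says something about the care used over the next ten weeks. If it does so beyond what site, age and fracture complexity already explain, two things follow. The cost difference, and hence INMB and the acceptability curve, carry more variance than the collected data require. And in the one trial actually run, any chance imbalance in baseline health leaves a shift in the cost component. The protocol names the covariate and confines it to one model without giving a reason, so this is a choice the document makes and not a detail it leaves open.

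**Working it through.** **1. The number of patients.** The protocol gives no cost SD, no SD for baseline utility and no cost-utility correlation. The one usable figure is the number with complete data in section 12.1: 204, or 102 per arm. It reproduces. With SD 21.9, difference 10, two-sided 0.05 and 90% power, the normal approximation gives 101 per arm; the exact t calculation gives power 0.898 at 101 and 0.901 at 102. It serves here only to size a chance imbalance.

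**2. Why QALYs need the covariate.** With utilities at baseline, 4, 5 and 10 weeks and linear change between them, the baseline score has weight (4/2)/52 = 2/52 = 0.0385 in the QALY. One unit of imbalance is then worth £20,000 x 2/52 = £769, or £30,000 x 2/52 = £1,154. The protocol's QALY adjustment already removes this. Cost has no such built-in term; baseline utility matters there only if it predicts cost.

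**3. Shift in the cost difference.** Assumptions: cost SD £800; correlation r between baseline utility and cost, given the other covariates, of -0.1 to -0.3; 102 per arm.

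- SE of the cost difference = 800 x sqrt(2/102) = £112.
- Shift from a 1-SE imbalance in baseline utility = |r| x £112.
- Share of cost-difference variance removed by adjustment = r².

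| r | shift | shift in SE units | cost variance removed |
|---|---|---|---|
| 0 | £0 | 0 | 0% |
| -0.1 | £11 | 0.1 | 1% |
| -0.2 | £22 | 0.2 | 4% |
| -0.3 | £34 | 0.3 | 9% |

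With 138 per arm (the synopsis total of 276) the SE is 800 x sqrt(2/138) = £96 and the shifts are £10 to £29. In SE units they are unchanged.

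**4. Effect on INMB at £20,000 per QALY.** Further assumptions: QALY SD 0.03, correlation 0.5 with baseline utility. In 4,000 simulated trials per value of r, the INMB variance with both models adjusted, divided by that under the protocol's models, was 0.993, 0.974 and 0.950 for r = -0.1, -0.2 and -0.3: a cut of about 1% to 5%. A closed-form check treats QALY and cost residuals as independent. The adjusted QALY term contributes (20,000 x 0.03)² x (1 - 0.25) = 270,000 and cost contributes 800² = 640,000, so the cut is 640,000 x r² / 910,000 = 0.7%, 2.8% and 6.3%, before a loss of about half a percent for the extra coefficient. The two agree closely; the top end is 5% to 6%.

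**5. Check for bias under different assumptions.** 10,000 simulated trials per scenario: baseline-utility SD 0.25, residual cost SD £500, 102 per arm, true INMB £30 at £20,000 per QALY.

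| cost slope per unit of utility (correlation) | mean INMB, protocol / both adjusted | SD of INMB, protocol / both adjusted | shift per 1-SE imbalance, protocol |
|---|---|---|---|
| 0 (0) | 28.9 / 28.9 | 89.8 / 89.9 | about £0 |
| -£100 (-0.05) | 30.3 / 30.4 | 88.6 / 88.7 | about £3 |
| -£300 (-0.15) | 30.8 / 30.6 | 89.5 / 89.1 | about £10 |
| -£1,000 (-0.45) | 28.7 / 28.9 | 96.3 / 89.9 | about £35 |

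The simulation error of each mean is about 90/sqrt(10,000) = £0.9, so both specifications centre on £30. With both models adjusted the shift is about £0 throughout. A clear difference in SD (96.3/89.9 = 1.07, or 7%) appears only at the steepest slope.

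**The case against.** The strongest defence is that the asymmetry has a reason. Baseline utility is arithmetically part of the area under the curve, so QALYs must be adjusted for it; cost counted from randomisation contains no such component. Different covariates in the two equations are legitimate, sections 12.2.3 and 12.4 agree, and whatever is lost on the cost side depends on a correlation the protocol does not report. All of this stands. It explains why QALYs need the covariate; it does not explain why costs should go without it.

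Three stronger readings are tempting, and the documents do not support them.

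- **That INMB is biased or the plan contradicts itself.** Under randomisation each difference is unbiased, so their combination is too, as step 5 of the working shows. What remains is precision and a shift conditional on the imbalance that happens to occur.
- **That the shift rivals the cost difference under study.** Section 3 gives £52.39 for a boot and £20.84 for plaster materials, a gap of £31.55, close to the largest shift above. But that gap concerns materials only. The NHS and social services cost in sections 7.4 and 12.4 also covers admissions, outpatient visits, therapies, tests, and community and social care, and the protocol nowhere says what difference it expects. The fair yardstick is the SE.
- **That nothing else guards against imbalance on the cost side.** The cost model already has site, age and fracture complexity; section 12.2.1 compares baseline EQ-5D between arms; and the sensitivity analyses in section 12.4 are open-ended enough to admit a cost model with baseline utility. None of them names that model, however. The planned addition of covariates that differ by chance (section 12.2.2, item d) is extended to secondary outcomes and not expressly to costs.

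Whether the two equations are fitted jointly or refitted on the same bootstrap samples is properly left to the analysis plan and is not part of this point.

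**Conclusion.** The point holds as a minor one. The protocol leaves out of the cost regression a baseline value that it collects before randomisation and already uses for QALYs. If that value predicts later cost given site, age and fracture complexity, the cost difference and INMB lose a little precision, and a chance imbalance stays in the cost component. The sizes in the working (shifts of 0.1 to 0.3 SE, INMB variance about 1% to 5% larger than needed) rest entirely on an assumed cost SD, QALY SD and correlation range. A weaker relation makes them negligible; only a correlation near -0.45, outside the range assumed for those figures, makes the loss plain. The direction of the advice is the same throughout, because including the covariate costs essentially nothing even when it predicts nothing.

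**What to change.** In section 12.4, reword the sentence so that the cost and QALY regressions each adjust for site, age, fracture complexity and baseline utility. Leave the method of joint fitting to the analysis plan.

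The cost is one phrase and one extra coefficient in the cost model. No new data are needed. The complete-case INMB loses no patients, because a patient without a baseline utility has no QALY either. If the sponsor prefers to keep the present cost model as the main one, the version with baseline utility could instead be named in advance as a sensitivity analysis.

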13. ETHICAL, REGULATORY, ADMINISTRATIVE AND QUALITY ASSURANCE

13.1. Ethical considerations

This trial was designed around the patient pathway and the usual management of ankle fractures within National Health Service Trusts, and therefore raises no special ethical issues. Staff will be trained in Good Clinical Practice which will be followed at all times.

An application for ethics approval will be made to a National Research Ethics Service Committee (REC). The trial will not proceed until Ethics approval and Trust approval from each participating site is obtained. Any amendments to the protocol will be submitted for REC approval and local NHS approval as appropriate.

Annual progress reports will be submitted to the REC using the recognised National Research Ethics Service (NRES) template. An end-of-trial declaration will be provided to the REC within 90 days of trial conclusion or within 15 days of trial termination in the event the trial is prematurely terminated.

Since the trial involves no Investigational Medicinal Product or non-CE marked medical devices, authorisation from the Medicines and Healthcare products Regulatory Agency will not be sought.

13.2. Declaration of Helsinki

The trial will be conducted in accordance with the ethical principles that have their origin in the Declaration of Helsinki, and that are consistent with GCP.

13.3. Research Governance

This trial will adhere to the principles outlined in the International Conference on Harmonisation Good Clinical Practice (ICH GCP) guidelines. It will be conducted in compliance with the protocol, NHS Research Governance Framework for Health and Social Care (2005 2nd edition) and other regulatory requirements as appropriate.

13.4. Study Management

The Trial Manager will co-ordinate the study (overseen by the Chief Investigator, supported by the Bournemouth University Clinical Research Unit and Peninsula Clinical Trials Unit). The Peninsula Clinical Trials Unit is a United Kingdom Clinical Research Collaboration registered Clinical Trials Unit and will conduct randomisation and manage the data following their Standard Operating Procedures.

Bournemouth University will support both the quantitative and qualitative analysis, the University of Bristol will support economic analysis, and Peninsula Clinical Trials Unit will provide randomisation, data management services and senior trial management support. The CI will be responsible for the overall running of the trial and will be in regular contact with PIs at the other participating sites.

The Trial Management Group (TMG) chaired by the Chief Investigator, will include all co-applicants, Trial Manager and service user representatives. The TMG will take responsibility for monitoring progress, ensuring development of documentation and forms, monitoring participant recruitment, follow-up and budget, discussing analysis, results, draft reports and dissemination. The TMG will meet regularly prior to the start of the study, and then in person every six months and remotely in between. There will be no Data Monitoring Committee (DMC) since both treatments are used in clinical practice.

13.5. Trial Steering Committee

The Trial Steering Committee (TSC) is responsible for the overall supervision of the trial, including overseeing recruitment, ensuring milestones are achieved and general scientific probity is maintained. In the absence of the DMC, the TSC will take on the role of reviewing adverse events, maintaining safety and will make recommendations for the premature discontinuation of the study where necessary.

The TSC will be chaired independently and will comprise of 6 full members; 3 independent experts (clinician(s)/statistician(s)), the Chief Investigator, and a service user representative. The Trial managers, data manager, sponsor and a funder representative will be invited to TSC meetings as observers. Members will meet at least annually as part of the Trial Steering Committee and will follow functions according to the Medical Research Council Good Clinical Practice guidelines³³. The composition and function will be described in a TSC charter prepared prior to study commencement.

